8.3 Randomisation method

Once enrolled in the study (provision of informed consent), patients will be randomised to standard care or Omegaven in a simple randomisation (1:3 allocation ratio) in each dosing phase. Randomisation will be performed using an electronic randomisation system embedded within the bespoke online trial database. Please see section 16.6 for more details regarding database.

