The BOIN intervention algorithm for the HIPPO trial is shown in **Figure 2**. ³⁵ ³⁶ Cut-offs for the escalation and de-escalation boundaries for the DLT rate were obtained using software available at www.trialdesign.org, using the following input parameters:

- three doses
- target toxicity rate for the maximum tolerable dose 0.30 (30%)
- patients recruited in cohorts of nine,
- maximum sample size is 27
- 0.80 probability cut-off for overdose control

Upon the completion of each dosing phase (defined as at least five hours after the last patient in the phase has finished the last dose of Omegaven), the DLT rate will be computed as follows, and compared with the cut-offs shown in **Figure 2** before treating the next cohort of patients:

DLT rate = Number of patients who experienced DLT at current dose

Total number of evaluable patients treated on current dose

Following the DLT assessment and based on the DLT rate, the next nine intervention patients will either:

- 1) receive the next highest dose if the observed DLT rate on the current dose is ≤0.236
- 2) remain on the same dose if the observed DLT rate is >0.236 and <0.359
- 3) de-escalate to the next lowest dose if the observed DLT rate is >0.359

If de-escalation is indicated on the lowest dose, the next cohort of patients will continue at the lowest dose. If the probability of the observed DLT rate being greater than the target DLT is >0.80 and if at least three patients are treated at the current dose, the dose is too toxic. Therefore, this dose and any higher doses will be eliminated. If the lowest dose is too toxic, the trial must be terminated.

After the panel meeting that will be held following completion of each dosing phase, a report will be drafted and agreed on by all panel members in a timely manner. The report which will include the recommended dosing plan for the next cohort of patients will be signed off by the trial statistician within two weeks of receipt. Once these approvals are in place, the next cohort of patients will be recruited. These approvals will be filed in the ISF and TMF. Each DLT assessment report will also be reported to the Data Monitoring and Ethics Committee (DMEC) for information only.

[figure not shown]

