3.0 Patient Evaluability and Replacement

3.1 Target Accrual

36 patients aged 18 years and over admitted to the Adult Critical Care Unit at The Royal London Hospital, Barts Health NHS Trust (27 participants randomised to Omegaven arm and nine participants randomised to standard care).

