5.0 Participant allocation

Since the trial involves an IMP that is unlicensed in UK, the PI or delegated doctors will be required to confirm eligibility of patients identified by the research team in the medical notes prior to approach. Following written informed consent, the patient will be randomised to either the standard care or Omegaven arm in blocks of 12 patients per dose-escalation phase. All randomised patients will be recorded on the study enrolment log with their trial ID.

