15.0 Statistical and data analysis

15.1 Sample size calculation

A total of 36 participants will be recruited (randomised 1:3 control:intervention). The number of participants treated on each dose of Omegaven will be determined by the escalation / deescalation rule specified in the BOIN design shown in Figure 2 and Table 1, which aims to exclude a toxicity rate of ≥ 30%. The minimum number of participants to be treated on a single dose is nine and the maximum is 27. Assuming mortality of approximately 20-30% in critically ill patients, we will replace up to a maximum of three patients in each study phase in case of patient death, or withdrawal. There is no formal assessment of sample size required for a phase I dose escalation trial, however 36 participants (nine control and 27 intervention) will be sufficient to provide pilot data on the exploratory outcomes. A published study with eight patient samples per group enabled examination of the p38 inhibitor and identification of a doubling in proliferation and cytotoxicity as measured by granzyme and perforin expression using nine patients per group would provide almost 80% power to detect a mean difference of 12 in %CD107a CD8+ EMRA T cells (assuming SD=6 and α=0.05) (unpublished data, [name])¹⁵. Early phase trials often use less conservative type I error rates as they can be considered screening studies to inform a future definitive trial; with this sample size the trial would have 87.4% power for α =0.1 and 94.4% for α =0.2 using the parameters given above.

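### Sections 5.0 and 8.3 specify different randomisation methods, and simple randomisation as in 8.3 would not secure the planned nine Omegaven and three control patients per phase

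*Protocol*

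**What the plan says.** Two sections of the protocol describe how patients are allocated.

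- Section 8.3 (Randomisation method): "patients will be randomised to standard care or Omegaven in a simple randomisation (1:3 allocation ratio) in each dosing phase".
- Section 5.0 (Participant allocation): "the patient will be randomised to either the standard care or Omegaven arm in blocks of 12 patients per dose-escalation phase".

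Other sections fix the numbers that allocation has to deliver.

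- Section 2.6 sets up the BOIN design with "patients recruited in cohorts of nine", and for the intervention the "maximum sample size is 27".
- Section 3.1 gives "27 participants randomised to Omegaven arm and nine participants randomised to standard care", 36 in all.
- Section 15.1 states: "The minimum number of participants to be treated on a single dose is nine and the maximum is 27".
- Section 15.4 plans an exploratory comparison of the laboratory outcomes at each dose against the controls randomised concurrently.
- Sections 9.0, 15.1 and 15.14 allow up to three patients per phase to be replaced. None of them says how a replacement is allocated.

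**The concern.** Under simple randomisation each patient is an independent draw, here with probability 0.75 of Omegaven, so the split within a phase is random. A block of 12 at 1:3 contains exactly nine Omegaven and three control allocations. A randomisation system cannot do both, and no other section of the protocol says which is meant.

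Two things depend on the answer. The first is the size of each Omegaven cohort: the dose decision is read from Table 3 by the number of evaluable patients treated, and section 15.1 sets a minimum of nine on a dose. The second is the number of concurrent controls. With about three expected per phase, chance could leave a dose with one or none for the comparison in section 15.4 and for the comparison of DLT event rates with controls in section 2.6.

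**Working it through.** **Inputs.** Allocation 1:3, so P(Omegaven) = 0.75 (8.3, 15.1). Three phases and 36 patients, so 36/3 = 12 per phase, which agrees with the blocks of 12 in 5.0. Cohort of nine and intervention maximum of 27 (2.6). Target toxicity rate 0.30 and overdose cut-off 0.80 (2.6).

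**The plan's own figures.** Three blocks of 12 at 1:3 give 3 × 9 = 27 Omegaven and 3 × 3 = 9 control, 36 in total. This matches sections 2.6, 3.1 and 15.1 exactly. The stated totals are therefore those of a blocked design.

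**Simple randomisation, phase closed at 12.** Let X be the number on Omegaven, X ~ Binomial(12, 0.75).

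- P(X = 9) = 220 × 0.75^9 × 0.25^3 = 0.258. For all three phases: 0.258^3 = 0.017.
- P(X < 9) = 0.351, against the stated minimum of nine on a dose. P(X > 9) = 0.391.
- P(X = 8) = 0.194 and P(X = 10) = 0.232.
- P(no control) = 0.75^12 = 0.032. For at least one of three phases: 1 − (1 − 0.032)^3 = 0.092.
- P(at most one control) = 0.032 + 0.127 = 0.158. For at least one of three phases: 1 − (1 − 0.158)^3 = 0.404.
- Over 36 patients, Binomial(36, 0.75): P(exactly 27:9) = 0.152, and P(more than 27 on Omegaven) = 0.436.

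**Simple randomisation, phase continued until nine are on Omegaven.** The cohort is nine by construction. The number of controls is negative binomial, with mean 9 × 0.25/0.75 = 3 and SD √(9 × 0.25/0.75²) = 2. P(no control) = 0.75^9 = 0.075. The phase totals 12 with probability 0.194, so neither nine controls nor 36 patients overall is assured.

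**Does the dose rule survive a cohort other than nine?** Yes. Table 3 has a column for every evaluable number from 3 to 27. Its rows can be rebuilt from the target 0.30 and the cut-off 0.80, taking the usual BOIN settings of 0.6 and 1.4 times the target and a uniform prior (assumed; the protocol does not state them). The boundaries come to 0.2365 and 0.3585, against the stated 0.236 and 0.359, and every column of Table 3 is reproduced.

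**Does cohort size change the decision?** It can. From Table 3:

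| Patients with DLT | n = 8 | n = 9 | n = 10 |
|---|---|---|---|
| 2 | stay | escalate | escalate |
| 3 | de-escalate | stay | stay |
| 4 | eliminate | eliminate | de-escalate |

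Four patients with DLT at the lowest dose stop the trial at n = 9. At n = 10 the next cohort is treated at that same dose (section 2.6, notes b and d to Table 3).

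**The case against.** The strongest reply is that this is a slip of wording. The blocks in 5.0 and the fixed 27 + 9 show what was intended, 'simple' may loosely mean unstratified, and sections 16.2 and 16.6 leave the database detail to a separate specification. That is plausible, but the protocol does not say so, and the section headed as the randomisation method says the opposite.

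Several stronger readings are tempting, and the protocol does not support them:

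- *That simple randomisation breaks the BOIN design.* It does not. The DLT rate is computed on evaluable patients, Table 3 defines a decision for each number from 3 to 27, and death or withdrawal can already move the evaluable number off nine.
- *That the 25.8% follows from 8.3 alone.* It also needs each phase to close at 12, which 8.3 does not say. Section 2.6 describes the next cohort as nine intervention patients, which could mean recruiting until nine are reached.
- *That section 15.4 requires three concurrent controls per phase.* It gives no number. The comparison is exploratory, and the primary outcome uses no controls.
- *That a replacement would be a fresh 1:3 draw, with a one in four chance of landing in control.* No mechanism is stated, so this is inference.

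What stands is that the two sections conflict, and that under 8.3 at least one stated target is left to chance whichever way a phase is closed.

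**Conclusion.** The concern holds as an internal contradiction with practical consequences. It is not a failure of the dose-escalation rule or of the analysis of the maximum tolerable dose.

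If 8.3 were implemented with phases closed at 12, the planned 9:3 split would occur in about one phase in four, the stated minimum of nine on Omegaven would be missed in about one phase in three, and the stated 27:9 total would be met about 15% of the time. If phases ran until nine were on Omegaven, the cohort would be safe, and the control count and overall total would vary instead. These figures take no account of replacements.

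Cohort sizes of 8 or 10 produced by allocation chance can alter an escalation or elimination decision. Unlike variation from death or withdrawal, this variation is avoidable.

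**What to change.** Delete 'simple' from section 8.3 and put one identical description in 5.0 and 8.3: concealed permuted-block randomisation at 1:3 within each dosing phase, giving nine Omegaven and three control allocations per 12 patients. One block of 12 or several smaller blocks (for example three of four) achieves this. Before replacements, it delivers 9:3 in every phase and 27:9 over 36 with certainty.

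State also how replacement patients are allocated, in a way that keeps the next allocation concealed. Refilling each arm from its own reserve list would not do this: in an open-label, single-centre trial the replacement's arm would be known before enrolment.

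The cost is a protocol wording change and a check that the randomisation specification, and the system if already built, agrees with it. The statistical price is that the last allocations in a block become more predictable when treatment is open. Section 5.0 already accepts this by specifying blocks.

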8.4 Randomisation procedure

Patients will be randomised by a delegated member of the research team using the bespoke trial database. The database is accessible via the NHS computers on site, with access only given to delegated members of the research team. Following randomisation, confirmation email will be sent to the member of the research team randomising. This will be included in the patient's medical records and in the ISF. As this is an open label study, allocation is known to medical care team, since it is documented on the patient's medical record.

8.5 Blinding

This is an open label study. Therefore, no unblinding procedure is necessary. However, the independent adjudicators for DLT events will be blinded to study arm allocation. There is no requirement to unblind the independent adjudicators, as this is their only involvement in the trial.

8.6 Unblinding

As described above, no unblinding procedure are required due to the open label approach to this trial.

9.0 Participant, Study, and Site discontinuation

It is always within the remit of the clinician with the clinical responsibility of patient care to withdraw the participant from the study for appropriate medical reasons. This can be (but is not limited to) individual AEs, new information gained about a treatment, or if it is felt to be in the participant's best interest.

If a patient or their Personal Legal Representative withdraws consent at any time during the trial - this decision will be respected and will be abided by. Treatment will be stopped (if ongoing). All data up to the point of this decision will be retained in the trial. Data collection from medical records for this trial will continue unless declined by the patient or their legal representative. This is mentioned in the respective Information Sheets.

If a participant or their Legal Representative withdraws consent, they will be asked to provide a reason for withdrawal, although it is not necessary to provide this. Withdrawal from the trial will be documented in the patient's medical records, in the enrolment log and the database.

If a patient is withdrawn from the study, up to three patients per treatment phase will be replaced. A patient who has withdrawn from the study cannot re-enter the study, as treatment should be provided on 10 consecutive days.

10.0 Laboratories and samples

10.1 Central laboratories

William Harvey Research Laboratory

This is an academic laboratory at QMUL. Immunological and metabolic assessments will be performed here. These are not standard diagnostic tests; they are performed for research purposes only and are exploratory.

Commercial laboratory for omega-3 Index and FA profile

A Clinical Laboratory Improvement Amendments-certified external laboratory (OmegaQuant) will be used to measure the omega-3 index and the FA profile. Results of these tests are an exploratory outcome and will not impact trial progression. These are not standard diagnostic tests performed for research purposes only and are exploratory.

Barts Health NHS Trust Pathology laboratory

Routine clinical samples from which data will be collected (via Electronic Health Records) will be processed as per usual care.

10.2 Sample collection, labelling, and logging

Where possible, blood sample collection (approximately 40 ml of whole blood) will be at the time of routine blood sampling to minimise discomfort for the participant. All blood samples will be pseudo-anonymised with the participant's trial ID. Samples will be stored in the site's hospital fridge and freezer depending on the subsequent analysis.

The full sample, collection, labelling, logging and transfer will be documented in the study sample log. The trial coordinating team will provide a Sample Management SOP Optional consent will be obtained for leftover blood samples from the blood tubes taken to be stored for future closely related studies and analysis carried out once ethical approval is obtained. A section for 'optional consent' for this purpose has been included in the ICFs.

10.3 Sample transfer, chain of custody, and accountability

Samples will be routinely transferred from Barts Health NHS Trust to QMUL where they will be stored prior to analysis or transferred to contracted laboratories (OmegaQuant). A Material Transfer Agreements or equivalent will be in place for all material transfers, as well as contracts with couriers and laboratories. Sample transfer will be at a temperature required for sample storage and analysis and temperature will be monitored as per Sample Management SOP. Handling of the samples upon arrival at the laboratories will be documented. All samples will be logged upon receipt and the laboratory will ensure that the physical integrity of these samples have not been compromised in transit. If compromise has occurred, the trial coordinating team, as well as the Sponsor, will be informed of this. Upon receipt of samples, laboratory staff will ensure that all samples are accounted for as per sample log provided with the transfer.

10.4 Sample analysis procedures

Immunological and metabolic assessments will be performed in the laboratory at QMUL, procedures will be detailed in the laboratory manual. Omega-3 index and FA profile will be

analysed from dried blood spots at OmegaQuant using a proprietary methodology. To confirm the laboratory assessments are not standard diagnostic tests; they are performed for research purposes only. For further details, please see study specific laboratory manual. Samples used for these analyses will be destroyed during analysis (i.e. samples transferred to OmegaQuant will be destroyed during analysis there; samples transferred to QMUL for immunological and metabolic assessments will be destroyed during the analysis there).

10.5 Sample Storage Procedures

The samples will be stored in pseudo-anonymised form with the participant's trial ID written on the label. Samples will be stored at the appropriate temperature, please see the Sample Management SOP. Samples already collected will not be destroyed if a patient withdraws from the study. Samples not destroyed during analysis will be retained for a further 6 months after the EOT, in case data analysis prompts reanalysis of any samples.

10.6 Sample and result recording and reporting

Pseudonymised results will be shared on a password protected excel sheet with the CI and study team by secure electronic communication (email) after the last patient sample has been analysed.

10.7 Sample Management at End of study

Most samples will be destroyed during analysis. At the end of the study, remaining samples will be destroyed in accordance with the Human Tissue Authority's Code of Practice, unless a further ethics application will be made for any surplus samples. The Consent Form contains a section to ask for consent for surplus samples to be used in closely related future studies that are approved by regulatory bodies.

11.0 Trial medication

11.1 Name and description of investigational medicinal product(s) (IMPs)

The IMP is Omegaven emulsion for infusion (containing fish oil 10 g) in 100 mL vial and further details about the IMP can be found in the SmPC.

11.2 Legal status of Omegaven

Omegaven is an EU only licenced product. For the HIPPO trial, the drug will be imported from Germany as a German marketed product (MA34164.00.00), with a German commercial label

from the manufacturer's facility to Royal London Hospital Clinical Trial Pharmacy in the UK for the purposes of a clinical trial. Annex 13 compliant label will be applied at Royal London Clinical Trial Pharmacy.

11.3 Summary of Product Characteristics (SmPC)

The SmPC used for this trial is for the 10 g/100 ml Omegaven provided by Fresenius Kabi.

11.4 Drug storage and supply

EU-QP released finished marketed product with German marketed labels will be supplied by Fresenius Kabi directly to Clinical Trials Pharmacy, Royal London Hospital UK. Shipments to sites will be initiated and managed by the trial management team who will monitor Omegaven stocks at site and subsequently initiate re-supplies. Upon receipt of a shipment, Clinical Trials Pharmacy will check the condition of the contents, and whether the temperature during transit was acceptable. Thereafter, Omegaven will be transferred to and stored at the agreed out-of-pharmacy location in the Research room, which has restricted access and appropriate temperature monitoring. Please see IMP Management Plan for more details.

11.5 Supplier/ Manufacturer

Omegaven supply will be arranged by Fresenius Kabi via a sub-contracted third-party specialised logistics company, that will handle the customs clearance process for distributing the drug (shipment documentation, pick up, shipper packaging, temperature monitoring, and delivery to pharmacy at site). Upon MHRA approval, the final consignee which is site Clinical Trials Pharmacy will be able to receive and handle the Omegaven product. Since the product received by Barts Health NHS Trust is unaltered, QP certification within the UK would not be required.

The application of a trial specific clinical label (that comply with annex 13 requirements) to the German commercial product will be done by clinical trial site pharmacy via the regulation 37 exemption (MHRA). Therefore, no UK MIA(IMP) is involved and neither UK QP verification nor UK QP certification is required for labeled IMPs.

Once the product has been labelled as per Annex 13 guidelines it will become an IMP and will be transferred to the appropriate site location. Please see Table 4 for the HIPPO-Supply chain diagram.

Sponsor will ensure that IMPs are provided to study site(s) only after regulatory green light and formal regulatory release by Sponsor for use in a study (= Site Initiation & IMP release for use in a study by Sponsor).

Table 4: HIPPO-Supply chain diagram

Name	Function	Location
Fresenius Kabi	Manufacturer of Bulk Drug Product and primary packaging of Drug Product with German label. EU QP release in Germany/EU in primary packaging (commercially available German marketed finished drug product with German marketed labels) Provision of Transmissible Spongiform Encephalopathy Statement, Certificate of Analysis and Certificate of Conformity Ship the Drug Product from Germany to UK via third party	Fresenius Kabi Deutschland GmbH [name], Germany
Third party specialised logistics company	Subcontracted by Fresenius Kabi. Pickup of product from Fresenius Kabi, Germany. Oversee and execute customs clearance (shipment documentation, pick up, temperature monitoring) and delivery of the drug to Barts Health Clinical Trial Pharmacy.	Safe GmbH [name], Germany and/or Marken Time Critical Express GmbH [name], Germany
Royal London Hospital Clinical Trials Pharmacy	Receipt and labelling of drug product to comply with Annex 13 requirements (using the regulation 37 exemption) Releasing drug product for transfer to research team	Clinical Trials Pharmacy [name]
ACCU Research Team	Storage of Drug Product for HIPPO trial Dispensing of Drug Product to participants	ACCU Research Offices [name]

11.6 How the drug should be stored

The storage conditions for Omegaven as per the SmPC are specified as follows:

- 1) Do not store above 25°C
- 2) Do not freeze

